4 STUDY DESIGN

4.1 OVERALL DESIGN

This is a pilot pragmatic observational study of usual care quality-of life outcomes at 3- and 6-months among adults seen in a tertiary care epilepsy clinic. It is a feasibility pilot designed to specifically assess feasibility (retention) of a novel, EMR-based outcome assessment method among 30 adults with epilepsy and high or borderline anxiety and/or depression symptoms. Participants will be randomized 1:1 to either a traditional pragmatic outcome collection method (telephone interview) versus the EMR-based outcome assessment method. We will consider the EMR-based outcome assessment feasible if 60% of subjects in this arm are retained at 6 months. We will also assess retention in the telephone based outcome arm.

The 3- and 6-month outcome assessment instruments are brief and freely available measures amenable to future pragmatic trial use in outcome assessments (QOLIE-10, GAD-7, NDDI-E). Secondary objectives of the study include generating preliminary estimates of effect of usual care on quality of life outcomes (primary) as well as anxiety and depression outcomes (secondary).

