9 STATISTICAL CONSIDERATIONS

9.1 STATISTICAL HYPOTHESES

- Primary feasibility hypothesis: We hypothesize that the primary endpoint, retention at 6 months in the EMR-based outcome assessment arm, will be greater than 60%.

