9.2 SAMPLE SIZE DETERMINATION

We are aiming to recruit 30 participants for the randomized outcome assessment feasibility study, with 15 in the EMR-outcome arm and equal allocation between EMR arm and the telephone arm. Using a

Bayesian design and a simulation study we assessed the probability of declaring acceptable adherence (80% credible interval that true adherence is at least 60%, $\Pr(X \geq 0.6) \geq 0.8$) over 10,000 simulated trials with sample size 15 in the intervention arm. We then summarized the results across all possible single trial outcomes and found if 11 to 15 subjects are retained, we are at least 83% confident that the true probability of retention is greater than 0.6. Thus, if at least 11 EMR arm participants meet the primary retention outcome, we will declare acceptable retention for using EMR based outcome assessment in future trials.

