9.4.2 ANALYSIS OF THE PRIMARY EFFICACY ENDPOINT(S)

The number of EMR-arm participants who meet retention criteria will be calculated, and as described above in the sample size determination section, if at least 11 EMR-arm participants meet the primary retention outcome, we will declare acceptable retention for using EMR based outcome assessment in future trials.

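### Two different go/no-go thresholds for the primary endpoint: Section 4.1 accepts 60% retained (9 of 15), Sections 9.2 and 9.4.2 require at least 11 of 15 (73%)

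*Combined protocol and SAP*

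**What the plan says.** Section 4.1 (Overall Design) gives a decision criterion on the share of participants retained: "We will consider the EMR-based outcome assessment feasible if 60% of subjects in this arm are retained at 6 months". It mentions no credible probability and no count, and does not refer to Section 9. Section 4.2 then says feasibility will be judged on EMR-arm retention as already described, which points back to Section 4.1.

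Section 9.2 (Sample Size Determination) sets the arm size, "with 15 in the EMR-outcome arm and equal allocation between EMR arm and the telephone arm", and the Bayesian criterion, "80% credible interval that true adherence is at least 60" percent, formally Pr(X ≥ 0.6) ≥ 0.8. It reports that "if 11 to 15 subjects are retained, we are at least 83% confident that the true probability of retention is greater than 0.6", and concludes that "if at least 11 EMR arm participants meet the primary retention outcome, we will declare acceptable retention".

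Section 9.4.2 (primary endpoint analysis) repeats the count: "if at least 11 EMR-arm participants meet the primary retention outcome, we will declare acceptable retention".

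Section 9.1 and the synopsis (1.1) state the hypothesis without a count. In 9.1 it reads "retention at 6 months in the EMR-based outcome assessment arm, will be greater than 60" percent.

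**The concern.** The figure of 60% does two jobs. In Section 9.2 it is the benchmark for the unknown true retention probability, and the data must show with posterior probability of at least 0.8 that this benchmark is met. In Section 4.1 it has become the cut-off for the observed proportion, which is a much weaker requirement: observing exactly 60% leaves roughly even odds that the true rate is above or below 60%.

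The primary objective is to decide whether EMR retention is good enough to use the method in future pragmatic trials, and this is the only decision rule for the primary endpoint. With 9 or 10 retained, the team could report success under Section 4.1 or failure under Section 9.4.2. Section 6.2 leaves the primary investigator and coordinator unblinded to arm, so the choice between the two rules could be made with the result in view.

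**Working it through.** **Inputs.** EMR arm n = 15 (9.2). Section 4.1 criterion: 60% observed. Sections 9.2 and 9.4.2 criterion: at least 11 retained. Bayesian criterion: Pr(true retention ≥ 0.6) ≥ 0.8 (9.2). Stated posterior at the cut-off: at least 83% (9.2). The prior is not stated. A uniform Beta(1,1) prior is assumed and varied below.

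**Step 1: counts.** 0.60 × 15 = 9. 11/15 = 73.3%. The counts on which the two rules disagree are 9 (60.0%) and 10 (66.7%).

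**Step 2: reproduce the plan's figure.** With prior Beta(a, b) and x of 15 retained, Pr(p > 0.6 | x) = 1 − F(0.6; a + x, b + 15 − x), where F is the Beta distribution function. With a = b = 1:

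| Retained | Posterior Pr(p > 0.6) | Meets 0.8? | Section 4.1 | Sections 9.2, 9.4.2 |
|---|---|---|---|---|
| 9 | 0.473 | no | feasible | not declared |
| 10 | 0.671 | no | feasible | not declared |
| 11 | 0.833 | yes | feasible | declared |
| 12 | 0.935 | yes | feasible | declared |

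The value at 11 matches the stated 83%, and 11 is the smallest count that passes. The Section 9.2 rule is internally correct.

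**Step 3: sensitivity to the prior.** Jeffreys Beta(0.5, 0.5), a near-Haldane prior, Beta(0.6, 0.4), Beta(1.2, 0.8) and Beta(3, 2) give 0.49 to 0.51 at 9, 0.69 to 0.72 at 10 and 0.84 to 0.88 at 11. Under each of them 9 and 10 fail and 11 passes, so the conflict does not depend on the assumed prior.

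**Step 4: how often the rules disagree and what each one does.** Let X be Binomial(15, p). P(9 or 10) = P(X ≥ 9) − P(X ≥ 11).

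| True retention p | P(X ≥ 9), Section 4.1 | P(X ≥ 11), Section 9 | P(9 or 10) | P(10 only) |
|---|---|---|---|---|
| 0.50 | 0.304 | 0.059 | 0.244 | 0.092 |
| 0.60 | 0.610 | 0.217 | 0.392 | 0.186 |
| 0.65 | 0.755 | 0.352 | 0.403 | 0.212 |
| 0.70 | 0.869 | 0.516 | 0.353 | 0.206 |
| 0.75 | 0.943 | 0.687 | 0.257 | 0.165 |
| 0.80 | 0.982 | 0.836 | 0.146 | 0.103 |

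The last column applies if Section 4.1 is read as strictly more than 60%, in line with the hypothesis in 1.1 and 9.1. Then 9 of 15 no longer passes and only 10 is disputed.

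**Step 5: dependence on n = 15.** Section 7.1 allows randomized participants who withdraw to be replaced while still being counted, unless they withdrew consent, so the arm may not end at 15. With a uniform prior the smallest passing count is 11 of 14, 12 of 16 and 13 of 17. Eleven of 16 gives 0.736 and would fail the 0.8 criterion.

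**The case against.** The best defence is that Section 9 governs. Section 9.4.2 is where the primary analysis is defined. It gives a single count, Section 9.2 derives that count and states it identically, and Section 9.2 already describes 60% as a benchmark for the true probability. Section 4.1 is one sentence in a design overview. Claiming success at 9 or 10 would visibly depart from 9.4.2, and because the observed percentage will be reported, readers can judge it for themselves. This is also a small pilot in which no participant's care depends on the label.

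Much of this is fair. Section 9 is the better-founded rule, which is why the fix adopts it, and a careful reader would probably prefer it. But Section 4.1 is worded as a decision criterion, not as a summary of one, and no clause gives Section 9 precedence. Being a pilot does not help either, because this go/no-go is the pilot's main product.

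A second objection is that 9 of 15 does not exceed 60%, so only 10 is in dispute. That narrows the conflict to 17% to 21% of trials at true retention of 60% to 75%, but does not remove it. It also adds a third candidate cut-off (9, 10 or 11).

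Two further points stand as limits on any rewording: the prior is not stated, and the count of 11 holds only for an arm of 15.

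**Conclusion.** The concern holds. Section 4.1 is wrong as written: it would declare feasibility on results that fail the plan's own criterion of 0.8. On its wording, the two rules give opposite answers for 9 or 10 retained, which has a probability of about 26% to 40% at true retention of 60% to 75%. At true retention of 60%, the chance of declaring feasibility is 61% under Section 4.1 and 22% under Section 9. At 50% it is 30% and 6%.

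The binomial figures assume 15 analysed in the EMR arm and independent participants. The posterior figures also assume a uniform prior, but the pass/fail pattern at 9, 10 and 11 was the same under every prior tried. The 11-of-15 rule itself is sound.

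**What to change.** Replace the Section 4.1 sentence with the Section 9.2 rule, for example: EMR-based assessment will be considered feasible if the posterior probability that true 6-month EMR retention is at least 60% is 0.80 or more, which with 15 participants means at least 11 retained (73%); see Sections 9.2 and 9.4.2.

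Add a clause in 1.1, 4.1 and 9.1 saying that 60% is the benchmark for the true retention rate, not the observed cut-off.

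In 9.2, name the prior (a uniform prior reproduces the stated 83%) and say that the posterior criterion decides if the arm does not contain exactly 15. Report the rule's operating characteristics there too: probability of declaring feasibility of 6%, 22%, 52% and 84% at true retention of 50%, 60%, 70% and 80%. These last figures are not needed to remove the contradiction, but they show readers how demanding the rule is.

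The cost is one sentence in 4.1, a few lines in 9.2 and a short clause in 1.1 and 9.1. Sample size, data collection and the Section 9 rule for an arm of 15 are unchanged. The only drawback is that the visible bar is 73% observed and not 60%.

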4.2 SCIENTIFIC RATIONALE FOR STUDY DESIGN

EMR-based tools to assess patient-reported outcomes are increasingly being proposed and used as a streamlined method for obtaining these patient reported measures and using them in care. In our previous pilot interventional study of neurologist treatment for anxiety and depression in epilepsy, we used IPad screening for anxiety and depression via REDCap to deliver standard care symptom screening and simultaneously screen individuals for potential research participation. This method required substantial coordinator effort to convey the screening results to clinicians for care purposes and to enter the results in the electronic medical record. Entry of patient reported measures directly into the electronic medical record has the potential to streamline clinical care while simultaneous pragmatic research is accomplished, because the instruments are entered as discrete data fields. Long-term outcome assessment via the patient portal interface of the electronic medical record may be feasible and potentially efficient for research staff.

In this study, we will screen patients for eligibility for the observational outcome study via implementation of standard care anxiety and depression screening and quality of life assessment directly into the patient entered section of the EMR, administered on arrival in the clinic. We will assess feasibility of EMR-based outcome assessment based on the primary endpoint of retention in the EMR-outcome arm as described above. We have decided to do a randomized feasibility trial comparing EMR outcome assessment to telephone outcome assessment, because the information from the telephone arm will also be valuable for future trial planning. This is because although telephone outcome assessment is often used in pragmatic trials, typical retention rates in epilepsy populations are unclear. Our study design aims to also assess retention using the telephone method in addition to the EMR method, to aid in determining future outcome assessment methods for interventional trials down the road. We will also use the quality of life and anxiety and depression outcome data at 3- and 6-months across the entire study population to generate estimates of long term effect of usual care among individuals with high or borderline anxiety and/or depression symptoms in epilepsy.

4.3 END OF STUDY DEFINITION

A participant is considered to have completed the study if he or she has completed all phases of the study including the last visit or the last scheduled procedure shown in the Schedule of Activities (SoA), Section 1.3.

The end of the study is defined as completion of the last visit or procedure shown in the SoA in the trial globally.

5 STUDY POPULATION

5.1 INCLUSION CRITERIA

In order to be eligible to participate in this study, an individual must meet all of the following criteria:

1. Male or female, age 18 or older
2. Adequate cognition (able to complete NDDI-E and GAD-7 independently in clinic)
3. Diagnosis of epilepsy: EEG with documented seizure or epileptiform discharges OR non-epileptiform EEG and seizure remission with antiseizure drug OR treating epilepsy specialist's leading clinical impression is epilepsy
4. NDDI-E score >13 AND/OR GAD-7 score >7 at regular clinic visit at the Wake Forest Comprehensive Epilepsy Center

5.2 EXCLUSION CRITERIA

1. High risk passive suicidal ideation score on NDDI-E: score on item 4 (I'd be better off dead) of 3 or 4 (sometimes OR always or often, respectively)

5.3 SCREEN FAILURES

Screen failures are defined as participants who consent to be screened for the study but are not subsequently randomly assigned or entered in the study. A minimal set of screen failure information is required to ensure transparent reporting of screen failure participants, to meet the Consolidated Standards of Reporting Trials (CONSORT) publishing requirements and to respond to queries from regulatory authorities. Minimal information includes demography, screen failure details, eligibility criteria, and any serious adverse event (SAE).

Individuals who do not meet the criteria for participation in this study (screen failure) because of a lack of current clinically significant anxiety or depression symptoms or other reasons may be rescreened.

5.4 STRATEGIES FOR RECRUITMENT AND RETENTION

- Target study sample size: 30 to be randomized; up to 40 consented. Anticipated number of participants to be screened: up to 1000
- Anticipated accrual rate: 5 per month

- Number of sites: 1
- Recruitment venue: clinic of Wake Forest Comprehensive Epilepsy Center, adult-focused epilepsy practices
- Participants will be identified using a learning health system care model which includes ALL patients completing the GAD-7, NDDI-E and QOLIE-10 instruments as a part of standard care upon check-in for a regular clinic visit. This will occur via a link from the clinic visit workspace to questionnaires in the patient portal interface (mywakehealth). Those who have borderline or high anxiety or depression (GAD-7 > 7 or NDDI-E >13) will be prompted to answer a question about interest in research.
- An inbasket message to study team will be triggered if an adult's GAD-7 and/or NDDI-E scores meet eligibility criteria and the individual indicates potential interest in research by answering yes to the following prompt.
 - We are doing a research study to see how patients in the epilepsy clinic with possible symptoms of anxiety or depression are doing 6 months after a clinic visit. The study includes one phone call over the next few days. Then in 3 and 6 months, you would answer some questions similar to those you just finished. Each time might take 5-10minutes.

May we contact you to tell you more about this study if you are eligible?

- When study staff receive the inbasket message, the medical chart will then be reviewed to assess whether a diagnosis of epilepsy is present. If epilepsy is present, the potential participant will be contacted by telephone and consent process will be initiated over the phone.
- For those eligible individuals who complete telephone consent for study participation, a brief baseline telephone interview focused on past psychiatric treatment history will be completed and the participant randomized. If necessary, mywakehealth activation will be done at the time of enrollment. Instructions for the allocated outcome assessment process will be provided.
- Multiple reminders and communications will be utilized to enhance participation in the outcome assessments. Telephone calls will be scheduled at the time of enrollment if possible. The outcome instruments will be mailed to telephone arm participants 10 days before scheduled outcome calls, and they will be sent electronically 10 days prior to target completion date for EMR-arm participants. Two telephone reminders for telephone arm participants, and two electronic reminders for EMR-arm participants will be provided prior to scheduled outcome assessment. Up to 5 attempts to call participants in the telephone outcome assessment arm will be made on separate days, starting at the originally scheduled outcome assessment time. Up to 5 electronic reminders with survey instructions will be sent via the EMR to the EMR arm participants, starting with target date for EMR outcome completion.
- After criteria for retention outcome at 6 months is met (5 reminders after due date for outcome assessment as described above), to reduce potential missing data for the secondary outcomes of 6-month change in quality of life, anxiety and depression, the following will be done. For any EMR-arm participants without successful 6-month outcome collection, 3 attempts will be made to collect outcomes via telephone. For any telephone arm participants without successful 6-month outcome collection, 3 attempts will be made to collect outcomes via EMR.
- Subjects will receive incentive of \$15 gift card for completing the brief baseline telephone interview and \$15 for completing each of the two outcome assessments (3 and 6 months).
- Efforts will be made to recruit any eligible participant seen in the practice, including women and under-represented populations

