3 OBJECTIVES AND ENDPOINTS

OBJECTIVES	ENDPOINTS	JUSTIFICATION FOR ENDPOINTS

Primary
 
To assess whether retention in the EMR-based outcome method arm at 6 months is sufficient in pilot testing to support use of this outcome assessment method in future pragmatic trials of management interventions for anxiety and depression in epilepsy.
	
-% retention in the EMR outcome arm, defined as the % of participants who complete the 6 month outcome instruments in the EMR
	
-obtain realistic estimate of feasibility of long-term EMR-based outcome assessment in this population

OBJECTIVES	ENDPOINTS	JUSTIFICATION FOR ENDPOINTS
Secondary		
To quantify retention at 3-and 6-months in the study population using a standard pragmatic trial outcome measure (telephone outcome assessment), and at 3 months using the EMR based outcome assessment method.	
-% retention at 6 months in the telephone outcome arm, defined as the % of participants who complete the 6 month outcome instruments via telephone
 
-% retention at 3 months in the EMR outcome arm, defined as the % of participants who complete the 6 month outcome instruments via telephone
 
-% retention at 3 months in the telephone outcome arm, defined as the % of participants who complete the 6 month outcome instruments via telephone
	
-to estimate future retention & develop retention strategy
 
-to assist in determining whether future studies should include telephone-or EMR-based outcome assessment for shorter and longer outcome assessment durations

To estimate 6-month change in epilepsy-specific quality of life (QOLIE-10, primary outcome) and depression and anxiety (secondary) at 3 and 6 months during usual care, among the feasibility cohort of individuals with epilepsy and borderline to high anxiety or depression scores at baseline.	
--6 month change in QOLIE-10 from baseline
 
--3 month change in QOLIE-10 from baseline
 
--change in anxiety (GAD-7) score from baseline to 3 and 6-month outcome assessments
 
--change in depression (NDDI-E) score from baseline to 3- and 6-month outcome assessments
	
-to generate preliminary estimates of effect for change in quality of life (and anxiety and depression) at 3- and 6-months from baseline during usual care, inputs that will be important for future trial planning with likely usual care control group

Tertiary/Exploratory		

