7.2 LOST TO FOLLOW-UP

A participant will be considered lost to follow-up if he or she fails to complete the 6-month outcome assessment and is unable to be contacted by the study staff.

The following actions must be taken if a participant fails to complete an outcome assessment appointment:

- Study staff will attempt to contact the participant and reschedule the missed outcome assessment within <1 week and counsel the participant on the importance of maintaining the assigned visit schedule and ascertain if the participant wishes to and/or should continue in the study.
- Before a participant is deemed lost to follow-up, the investigator or designee will make every effort to regain contact with the participant (where possible, 5 telephone calls or electronic communications in the EMR as outlined above followed by up to 3 attempts by the alternative modality (following primary retention outcome assignment as described in recruitment and retention section) and, if necessary, a certified letter to the participant's last known mailing address or local equivalent methods). These contact attempts will be documented in the participant's study file.
- Should the participant continue to be unreachable, he or she will be considered to have withdrawn from the study with a primary reason of lost to follow-up.

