8 STUDY ASSESSMENTS AND PROCEDURES

8.1 EFFICACY ASSESSMENTS

Screening Assessment

-NDDI-E, GAD-7, QOLIE-10³⁸

Implementation Monitoring:

RE-AIM framework measures

Feasibility assessments:

Enrollment/Baseline Assessments:

-accrual assessment

Retention: defined as outcomes collected via randomized modality within 1 week of the final of 5 scheduled reminders following outcome assessment due date (see recruitment and retention section for details of reminder process for each arm).

-6 month retention in EMR outcome arm

-6 month retention in the telephone outcome arm

-3 month retention in EMR and telephone outcome arms, respectively

Other feasibility assessments:

-# attempts to contact participants in each arm

-staff time for telephone outcome assessment/telephone contact attempts/preparing mailed survey packets vs staff time to send EMR surveys and electronic reminders

-time for participant completion of EMR surveys

-delay from survey delivery to completion by participant

Usual care outcome assessments (3 and 6 months):

- QOLIE-10
- NDDI-E
- GAD-7
- healthcare utilization (ED visits, hospitalizations)

Review of Clinical Chart: this will be done for preliminary eligibility assessment and for supplementary information on medications prescribed and health care utilization during the study period.

Health Insurance Portability and Accountability Act (HIPAA) rules, other relevant federal or state laws, and local institutional requirements will be followed, as applicable.

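### Section 5.4 permits 6-month cross-over attempts from the fifth reminder, but Section 8.1 counts completions by the allocated modality for one more week, so the two can overlap

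*Combined protocol and SAP*

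**What the plan says.** Section 8.1 gives the working definition of retention: "defined as outcomes collected via randomized modality within 1 week of the final of 5 scheduled reminders following outcome assessment due date". For details of the reminders it refers to the recruitment and retention section.

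That section, 5.4, describes up to five electronic reminders in the EMR arm and up to five call attempts in the telephone arm, counted from the due date. It then adds a rescue step to limit missing data on the secondary 6-month outcomes. The step begins "After criteria for retention outcome at 6 months is met (5 reminders after due date for outcome assessment as described above"). In the EMR arm it reads: "For any EMR-arm participants without successful 6-month outcome collection, 3 attempts will be made to collect outcomes via telephone". The telephone arm has the mirror image, with three attempts through the EMR.

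Section 7.2 repeats the order of events: contact by the allocated route, "followed by up to 3 attempts by the alternative modality (following primary retention outcome assignment as described in recruitment and retention section").

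Section 3 states the primary endpoint as EMR-arm retention, "defined as the % of participants who complete the 6 month outcome instruments in the EMR", with no closing time. Section 9.4.2 gives the decision rule: "if at least 11 EMR-arm participants meet the primary retention outcome, we will declare acceptable retention".

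**The concern.** The 5.4 parenthesis equates the met retention criterion with five reminders having been sent. It omits the further week in 8.1. Section 7.2 gives no time of its own and sends the reader back to 5.4, so the section that staff would follow for contact attempts is the one without the week.

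The primary question is whether collection through the EMR retains enough participants. If staff telephone an EMR-arm non-completer while a portal completion would still count, the modality under test is no longer working alone. Section 6.2 shows that the plan cares about this kind of influence: where possible it withholds the allocation from the treating provider so that clinical contact does not bias retention.

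**Working it through.** **Timing.** Both rules are anchored on the fifth reminder (in the telephone arm, the fifth call attempt), so the unstated spacing of reminders does not matter. Call that day 0 for a given participant.

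- Section 8.1: completion by the allocated modality counts from the due date up to day 7.
- Section 5.4, read literally: attempts by the other modality may start from day 0.
- Section 7.2: those attempts follow retention assignment, with timing taken from 5.4.
- Section 3: no closing time.

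The permitted overlap is therefore day 0 to day 7, at most one week per participant. No section tells staff to wait for day 7, and none tells them to start on day 0.

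**What a call in that week could do to an EMR-arm participant still outstanding on day 0.**

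- The participant would not have used the portal, and the call prompts a portal completion: the count rises by 1.
- The participant would have used the portal by day 7, but answers by telephone instead: the count falls by 1, because the response did not come by the allocated modality.
- Otherwise: no change.

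The documents give no rate for either of the first two cases, so neither the sign nor the size of a net effect can be derived.

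**When one participant matters.** Inputs from Section 9.2: 15 participants in the EMR arm, a retention target of 0.6, a required posterior probability of at least 0.8, and the statement "if 11 to 15 subjects are retained, we are at least 83% confident". The prior is not stated. I assume a uniform Beta(1,1), so with x retained the posterior is Beta(1 + x, 1 + 15 − x).

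- x = 11: Beta(12, 5), P(p ≥ 0.6) = 0.833. This reproduces the plan's 83%.
- x = 10: Beta(11, 6), P(p ≥ 0.6) = 0.671, below 0.8.
- x = 9: Beta(10, 7), P(p ≥ 0.6) = 0.473.

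A Jeffreys prior, Beta(0.5, 0.5), gives 0.855 at 11 and 0.695 at 10, so the cut-off is the same.

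One participant is 1/15 = 6.7 percentage points of retention. If 11 or more have already completed by their fifth reminder, the rule is met and later contact cannot undo it. With 10 completed by then, one change of status in the overlap week decides the outcome. With 9, two are needed.

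**Other endpoints.** The mirror-image step creates the same overlap for 6-month telephone retention, a secondary endpoint. Retention at 3 months is untouched, because 5.4 describes cross-over collection only at 6 months.

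**The case against.** The best defence is that the sections, read together, already settle the order. The main clause in 5.4 makes cross-over wait for the retention criterion, the only timed criterion is in 8.1, and 7.2 puts cross-over after retention assignment. Under 8.1 a non-completer cannot be assigned until the week has closed. On this view 5.4 describes the reminders, 8.1 defines retention, and the parenthesis is shorthand. That is probably what was meant. It does not remove the problem: the parenthesis states what the criterion is and leaves out the week, and 7.2 points to 5.4 for timing.

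The objection that overlap is only permitted also stands. Section 5.4 sets an earliest point for the attempts, and staff may in practice have waited.

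A reader might go further and infer that a portal completion in the disputed week could be scored either way, so that the same data give 10/15 or 11/15. The documents do not support that. Section 5.4 triggers rescue collection for secondary outcomes and is not a scoring rule. Section 9.4.2 counts those who meet the retention criteria, and 8.1 alone gives those a closing time, so such a completion is retained.

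Finally, the move from 0.671 to 0.833 is what any change of one participant does at the cut-off with n = 15. It shows where the overlap could matter. It does not measure the overlap's effect.

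**Conclusion.** The point holds as a minor inconsistency, with moderate confidence because the intended order is fairly clear. As written, 5.4 permits up to one week per participant in which staff may contact people by the other modality while completions by the allocated modality still count. The primary decision is exposed only if 10 or fewer of 15 EMR-arm participants have completed by their fifth reminder, and one participant is decisive only at 10. The posterior figures rest on an assumed uniform prior, which reproduces the plan's 83%.

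A reader might infer that EMR retention will be inflated, since calls tend to prompt responses. The documents do not support a direction, because a telephone answer can equally displace a portal completion that would have counted. The decision rule, the cut-off of 11 and the 83% figure need no change.

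**What to change.** In 5.4, replace the parenthesis so that attempts by the alternative modality, in both arms, start only once the 8.1 window has closed (fifth reminder plus 1 week) and the participant's retention status has been recorded. Section 7.2 then inherits the right timing through its reference to 5.4. Safety calls are unaffected.

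The cost is one clause, with no extra data, analysis or sample size. The downside is that rescue collection of the secondary 6-month outcomes starts up to one week later for participants still outstanding.
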